## 5.1. Adverse Events

The analysis of AEs will be based on the medical dictionary for regulatory activities (MedDRA) coded terms as will be provided in the clinical database.

### 5.1.1. Definitions

Solicited AEs shown in the tables will be extracted from the investigator assessment pages of the eCRF. The severity of all AEs will be classified as Grade 1 to 3. For unsolicited AEs, only the AEs within the 28-day period following each vaccination will be presented in the safety tables except for SAEs which will be captured and tabulated covering the entire study duration. A listing will also be generated for all collected unsolicited AEs.

Solicited local AEs will be considered (by definition) as related to the study vaccine. In case no grades are available, the grading of the solicited events will occur according to the grading list in Attachment 1.

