6.2. Contraindications to Second Vaccination

A participant will not be given the Dose 2 or booster dose vaccination if he or she experiences any of the following events at any time after the Dose 1 vaccination:

1. Anaphylaxis clearly attributable to vaccination with study vaccine; *OR*
2. Generalized urticaria within 72 hours of vaccination considered to be related to study vaccine; *OR*
3. A serious adverse event considered to be related to study vaccine; *OR*
4. Injection site ulceration, abscess, or necrosis considered to be related to study vaccine; *OR*
5. Any other safety concern threatening the participant's safety.

Participants experiencing any of the events described above must not receive any further study vaccine but should continue be monitored for safety and for immunogenicity according to the protocol if this does not result in safety risks for the participant.

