10.2. Discontinuation of Study Vaccine/Withdrawal From the Study

Discontinuation of Study Vaccine

A participant will not be automatically withdrawn from the study if he or she has to discontinue study vaccine before the end of the vaccine regimen.

A participant's study vaccine (Dose 1, Dose 2, or booster dose) may be discontinued at the discretion of the investigator and after consultation with the sponsor for any of the events in Section [6.1](#).

A participant's study vaccine should be **permanently** discontinued if:

- The investigator believes that for safety or reactogenicity reasons (eg, adverse event) it is in the best interest of the participant to discontinue study vaccine;
- The participant becomes pregnant;
- Confirmed EVD;
- The participant experiences any of the events described in Section [6.2](#);
- The randomization code is broken by the investigator or the study site personnel.

Participants meeting any of the reasons listed above must not receive any further study vaccine but should continue to be monitored for safety and immunogenicity according to the protocol if this does not result in safety risks for the participant. In case of early discontinuation of study vaccine due to an adverse event, the investigator will collect all information relevant to the adverse event

and safety of the participant, and will follow the participant to resolution, or until reaching a clinically stable endpoint.

Withdrawal From the Study

Each participant has the right to withdraw from the study at any time for any reason without affecting the right to treatment by the investigator. The investigator should make an attempt to contact participants who did not return for scheduled visits or follow-up. Although the participant is not obliged to give reason(s) for withdrawing prematurely, the investigator should make a reasonable effort to ascertain the reason(s) while fully respecting the participant's rights.

A participant will be withdrawn from the study for any of the following reasons:

- Lost to follow-up
- Withdrawal of consent
- Death
- Repeated failure to comply with protocol requirements
- Decision by the sponsor or the investigator to stop or cancel the study
- Decision by local regulatory authorities or IRB/IEC to stop or cancel the study

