12.3. Procedures

12.3.1. All Adverse Events

Solicited adverse events will be recorded in a diary for each vaccination from the moment of vaccination until 7 days post each vaccination.

All adverse events and special reporting situations, whether serious or nonserious, that are related to study-related procedures or to non-investigational (concomitant) sponsor products, and pregnancy (if applicable), will be reported from the time a signed and dated ICF is obtained onwards.

Other serious adverse events and special reporting situations will be reported from first dose of study vaccine until the end of the study.

Other nonserious adverse events and special reporting situations will be reported from first dose of study vaccine until 28 days after first dose of study vaccine, from the second dose of study vaccine until 28 days thereafter, and from the booster dose until 28 days thereafter (Groups 5-6 only).

Unsolicited adverse events with the onset date outside the time frame defined above (>28 days after previous study vaccination), which are ongoing on the day of the subsequent vaccination, should be recorded on the eCRF Adverse Event page.

Clinically relevant medical events occurring between signing of ICF and first vaccination will be collected on the eCRF Medical History page as pre-existing conditions.

The sponsor will evaluate any safety information that is spontaneously reported by an investigator beyond the time frame specified in the protocol.

The investigator will monitor and analyze the study data including all adverse event data as they become available and will make determinations regarding the severity of the adverse experiences and their relation to study vaccine. All adverse events will be deemed related to study vaccine or unrelated to study vaccine, according to Section 12.1.2.

The investigator or clinical designee must review both post-injection reactogenicity and other adverse event eCRFs to insure the prompt and complete identification of all events that require expedited reporting as serious adverse events, invoke pausing rules or are other serious and unexpected events.

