### 5.1.2. Analysis of Adverse Events

Number and percentage of participants with at least one particular AE (unsolicited/solicited) will be tabulated. Unsolicited AEs will be summarized by System Organ Class and Preferred Term. Solicited AEs will be summarized by class (local, systemic) and preferred term.

The following tables will be generated for solicited AEs: summary (ie, any solicited AE, solicited AE with Grade 3 severity, any solicited local AE, solicited local AE with Grade 3 severity, any solicited systemic AE, solicited systemic AE with Grade 3 severity, and solicited systemic AE considered related to vaccine), by worst severity grade, Grade 3, related (systemic only), time to onset (in days) and duration (in days) for most frequent events and body temperature. Note that duration is defined as number of days from the start of the event until resolution of the event. The time to first onset is defined as (date of first onset – reference date + 1). The reference date is the start date of the vaccination period.

For unsolicited AEs, the following tables will be generated: summary table (including any unsolicited AE, unsolicited AE with severity Grade 1 as worst grade, unsolicited AE with severity Grade 2 as worst grade, unsolicited AE with severity Grade 3 as worst grade, unsolicited AE considered related to vaccine, unsolicited AE leading to permanent stop of study vaccine, SAE, SAE considered related to vaccine, COVID-19 related AE, AEs with fatal outcome), all events, most frequent, Grade 3, AEs leading to permanent stop of vaccination, related and SAE.

Listings and/or participant narratives will be provided as appropriate, for those participants who die, discontinue study vaccination due to an AE, experience a Grade 3 AE considered related to vaccination, experience an SAE, experience a SARS-CoV-2 infection (COVID-19) or vaccine misallocation.

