### 5.1.3. Phase Allocation of Adverse Events

Solicited events are always allocated to the respective post-dose period. The AEs in the standard data tabulation model (SDTM) database will be allocated to periods based on their start date/time. If the start

date/time of an AE falls between (or on) the start and stop date/time of a period, the AE is attributed to that period (treatment-emergent principle). A stepwise approach to allocate AEs to the analysis periods/phases based on their start date/time is given in Attachment 2.

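### The SAP's 28-day limit keeps a later-onset nonserious event that stops the next dose out of the summary row and table of adverse events leading to permanent stop of vaccination

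*SAP*

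**What the plan says.** SAP 5.1.1 sets the rule for the tables: "For unsolicited AEs, only the AEs within the 28-day period following each vaccination will be presented in the safety tables except for SAEs". SAEs, the only exception, are tabulated over the whole study. The next sentence of 5.1.1 adds a listing of all collected unsolicited events.

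SAP 5.1.2 includes in the unsolicited-event summary table a row for "unsolicited AE leading to permanent stop of study vaccine". Among the further tables it names "AEs leading to permanent stop of vaccination, related and SAE". No separate time window is given for the events that stop vaccination.

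SAP 5.1.3 makes onset the deciding date: "The AEs in the standard data tabulation model (SDTM) database will be allocated to periods based on their start date/time". In SAP Table 3 each post-dose period ends at the latest 28 days after the dose. SAP 5 presents safety data for the post-dose periods and their combination. Table 3 also defines follow-up periods, but SAP 5 does not list them for presentation. Protocol 11.4 uses the same 28-day onset limit.

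The decision to stop vaccine has no such limit. Protocol 6.2 bars Dose 2 or the booster "if he or she experiences any of the following events at any time after the Dose 1 vaccination". Protocol 10.2 requires permanent discontinuation when the investigator believes, for safety or reactogenicity reasons, that "it is in the best interest of the participant to discontinue study vaccine".

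**The concern.** Events that end a participant's regimen are a standard tolerability result for a multi-dose vaccine. The natural moment for the decision is the next dosing visit, at least seven weeks after Dose 1 and about four months after Dose 2 for the booster. Participants are asked about unsolicited events at those visits. A nonserious event found then, with onset after day 28, is a discontinuation event in the ordinary sense, yet the tabulation rule removes it from the row and table named for such events.

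Two things are at stake. The breakdown by group, System Organ Class and preferred term may be incomplete. The adverse-event table may also show fewer event-related stops than the disposition table in SAP 4.2, which counts vaccination discontinuations by reason with no onset limit. A reader of the study report would then see two different counts. Safety of the two-dose regimen is a secondary objective, and protocol 1.3 says the study is meant to enlarge the safety package supporting approval. The primary endpoint is not affected.

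**Working it through.** **Inputs.** Doses fall on Day 1, Day 57 and, in Groups 5-6 only, Day 177 (protocol 6). Coverage runs to the dose day plus 28 (SAP Table 3). The Dose 2 window is Day 54 to Day 85 in Groups 1-4 and ±1 week in Groups 5-6; the booster window is ±1 week (protocol Time and Events Schedule).

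**Nominal intervals.** 57 − 1 = 56 days from Dose 1 to Dose 2; 177 − 57 = 120 days from Dose 2 to booster.

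**Formula.** First uncovered day = dose day + 29. Last uncovered day = next dose day − 1. Uncovered days = last − first + 1. Share = uncovered days ÷ interval.

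| Interval | Uncovered days | Count | Share |
|---|---|---|---|
| Dose 1 to Dose 2, nominal | 30 to 56 | 27 of 56 | 48% |
| Groups 1-4, Dose 2 on Day 54 | 30 to 53 | 24 of 53 | 45% |
| Groups 1-4, Dose 2 on Day 85 | 30 to 84 | 55 of 84 | 65% |
| Groups 5-6, Dose 2 on Day 50 | 30 to 49 | 20 of 49 | 41% |
| Groups 5-6, Dose 2 on Day 64 | 30 to 63 | 34 of 63 | 54% |
| Dose 2 to booster, nominal (Groups 5-6) | 86 to 176 | 91 of 120 | 76% |

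If both booster-cohort windows are counted from the nominal days, the Dose 2 to booster gap ranges from 77 of 106 days (Day 64 to Day 170, 73%) to 105 of 134 days (Day 50 to Day 184, 78%).

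**What the shares mean.** They are fractions of calendar time in which a new nonserious onset falls outside the table. They do not estimate the fraction of stopping events missed, because the documents give no event rates. An event that starts within 28 days and leads to a stop later is still counted, since onset decides.

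**Where an excluded event appears.** Take a nonserious event with onset on Day 40 that leads to Dose 2 being withheld.

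- Summary row and table of events leading to permanent stop (SAP 5.1.2): excluded by SAP 5.1.1.
- Listing of all collected unsolicited events (SAP 5.1.1): included.
- Listings and/or narratives for participants who stop vaccination because of an event (SAP 5.1.2): covered where judged appropriate; no onset limit is stated.
- Disposition table (SAP 4.2): counted by group as a vaccination discontinuation with its reason.

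**Collection rules side by side.** Protocol 12.3.1 gives separate 28-day reporting periods after each dose for other nonserious events, and adds that later-onset unsolicited events "which are ongoing on the day of the subsequent vaccination, should be recorded on the eCRF Adverse Event page". Protocol 9.1.2 and footnote o of the main schedule follow the same pattern. Footnote l of the booster schedule instead describes one continuous period from the first dose until 28 days after the booster. For Groups 5-6 the two texts disagree about Days 30 to 56 and Days 86 to 176.

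**The case against.** The best defence is that the rule is prespecified and consistent. The secondary safety endpoint is unsolicited events until 28 days after each vaccination, protocol 11.4 repeats that limit, and the SAP follows it. The disposition table already gives the per-group count of vaccine stops by reason, so only the System Organ Class and preferred term detail in one table is cut. That stands, and it limits the weight of the point. It does not remove it: the SAP already recognises that SAEs need tabulation over the whole study, and a table titled for events that stop vaccination does not deliver its title when late nonserious ones are excluded.

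Most of the contraindications in protocol 6.2 are also unlikely to arise late. Urticaria must occur within 72 hours of vaccination, and related SAEs are already exempt from the limit. What remains is mainly the general safety-concern item and the investigator's judgement under 10.2. This supports expecting few events.

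A reader might infer that these events escape recording altogether, because the late-onset rule depends on a subsequent vaccination that never takes place. The documents do not support that. Protocol 9.3.1 requires clinically relevant changes during the study to be entered on the Adverse Event page, 10.2 requires full information on an event that stops vaccine, and 12.3.1 requires all adverse events to be recorded in source and eCRF. The wording on collection periods is inconsistent, but loss of the data is not shown.

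A reader might also want the COVID-19 row of the same summary table ("unsolicited AE leading to permanent stop of study vaccine, SAE, SAE considered related to vaccine, COVID-19 related AE") extended to the whole study. Routine nonserious collection in Groups 1-4 ends 28 days after Dose 2, so such a row would mix systematic with incidental capture and look more complete than it is. SAP 5.1.2 already provides listings and/or narratives for SARS-CoV-2 infection.

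**Conclusion.** The point holds as a modest improvement to one summary row and one table. By rule they omit a nonserious event with onset more than 28 days after a dose that leads to the next dose being withheld. For the main study of at least 741 participants there is one such gap: nominally Days 30 to 56, and up to Day 84 within the widened Dose 2 window. Protocol 3.1 reports that about 22% did not return within ±3 days of Day 57, so gaps longer than nominal are realistic for some participants. The longer gap before the booster concerns only the booster cohort of about 60.

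The consequence is a possible undercount in that row and table and a possible mismatch with disposition. It does not follow that the study report as a whole understates stops for adverse events, since the disposition table has no onset limit. The conclusion rests on reading SAP 5.1.1 literally, which SAP Table 3, SAP 5, SAP 5.1.3 and protocol 11.4 all support. The number of affected events is not given and may be zero.

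**What to change.** 1. In SAP 5.1.1, widen the exception so that it covers SAEs and adverse events leading to permanent stop of study vaccine, both tabulated over the whole study. Apply this to the summary row and the table in 5.1.2, using the whole-study presentation already planned for SAEs, and footnote the different window.
2. In SAP 1.6, record the departure from the 28-day onset rule in protocol 11.4.
3. Reconcile the nonserious-event collection periods in protocol 12.3.1, 9.1.2 and main-schedule footnote o with booster-schedule footnote l, so that it is clear what is collected between doses in Groups 5-6.
4. Leave the COVID-19 row as it is.

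The cost is one SAP phrase, one note and one wording reconciliation, with no new visits and no change to any stopping rule. The downside is that the reported rate of events leading to vaccine stop may rise slightly, and this row will use a different time window from the other nonserious rows.

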### 5.1.2. Analysis of Adverse Events

Number and percentage of participants with at least one particular AE (unsolicited/solicited) will be tabulated. Unsolicited AEs will be summarized by System Organ Class and Preferred Term. Solicited AEs will be summarized by class (local, systemic) and preferred term.

The following tables will be generated for solicited AEs: summary (ie, any solicited AE, solicited AE with Grade 3 severity, any solicited local AE, solicited local AE with Grade 3 severity, any solicited systemic AE, solicited systemic AE with Grade 3 severity, and solicited systemic AE considered related to vaccine), by worst severity grade, Grade 3, related (systemic only), time to onset (in days) and duration (in days) for most frequent events and body temperature. Note that duration is defined as number of days from the start of the event until resolution of the event. The time to first onset is defined as (date of first onset – reference date + 1). The reference date is the start date of the vaccination period.

For unsolicited AEs, the following tables will be generated: summary table (including any unsolicited AE, unsolicited AE with severity Grade 1 as worst grade, unsolicited AE with severity Grade 2 as worst grade, unsolicited AE with severity Grade 3 as worst grade, unsolicited AE considered related to vaccine, unsolicited AE leading to permanent stop of study vaccine, SAE, SAE considered related to vaccine, COVID-19 related AE, AEs with fatal outcome), all events, most frequent, Grade 3, AEs leading to permanent stop of vaccination, related and SAE.

Listings and/or participant narratives will be provided as appropriate, for those participants who die, discontinue study vaccination due to an AE, experience a Grade 3 AE considered related to vaccination, experience an SAE, experience a SARS-CoV-2 infection (COVID-19) or vaccine misallocation.

### 5.1.3. Phase Allocation of Adverse Events

Solicited events are always allocated to the respective post-dose period. The AEs in the standard data tabulation model (SDTM) database will be allocated to periods based on their start date/time. If the start

date/time of an AE falls between (or on) the start and stop date/time of a period, the AE is attributed to that period (treatment-emergent principle). A stepwise approach to allocate AEs to the analysis periods/phases based on their start date/time is given in Attachment 2.

#### **5.1.4. Missing Data**

Missing data will not be imputed. Participants who do not report an event will be considered as participants without an event. An AE with a missing severity or relationship will be considered as an AE reported, but will be considered as not reported for the severity or relationship. For example, an AE with missing severity will be considered as an AE reported for the analysis of any grade, but will be considered as not reported for the analysis of Grade 3.

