12.1.2. Attribution Definitions

Every effort should be made by the investigator to explain any adverse event and to assess its potential causal relationship, ie, to administration of the study vaccine or to alternative causes (eg, natural history of underlying diseases, concomitant therapies). This applies to all adverse events, whether serious or nonserious.

Causality of adverse events should be assessed by the investigator based on the following:

Related: there is a reasonable possibility that the study vaccine contributed to the adverse event.

Unrelated: there is no suspicion that there is a relationship between the study vaccine and the adverse event; there are other more likely causes and administration of the study vaccine is not suspected to have contributed to the adverse event.

By definition, all solicited adverse events at the injection site (local) will be considered related to the study vaccine administration.

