### **5. SAFETY**

Safety analyses will be performed on the full analysis set. Frequencies and percentages (one decimal place) will be generated for the AEs. No formal comparisons between groups will be provided.

The safety data will be presented by vaccination group (as shown in [Table 2](#)). The data will be presented by analysis period (post-dose 1, post-dose 2, and post-booster [only for the booster cohort]) as well as over the entire regimen period (ie, combined post-dose 1 and post-dose 2 periods, and combined post-dose 1, post-dose 2 and post-booster [only for the booster cohort]). Denominator for the percentages will be the

number of participants in the considered analysis set and period/phase for a certain vaccination group (eg, incidence per 100 participants/period).

To evaluate the potential impact of delayed (due to COVID-19 pandemic) Dose 2 vaccination, safety data will also be presented (only if more than 10% of participants receive Dose 2 vaccination outside the widened window) for participants having received Dose 2 vaccination within the widened window (as defined in CTP Amendment 3) versus those having received Dose 2 outside the window.

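### SAP 5.1.4 drops an adverse event with a blank grade or causality from the Grade 3 or related numerator but keeps the full denominator, so those rates can be understated but never overstated

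*SAP*

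**What the plan says.** SAP 5.1.4 opens with "Missing data will not be imputed". For an adverse event lacking a grade or a causality assessment it then says: "An AE with a missing severity or relationship will be considered as an AE reported, but will be considered as not reported for the severity", and the sentence ends by extending the same treatment to relationship. The SAP's own example is an ungraded event, which counts for any grade but "will be considered as not reported for the analysis of Grade 3".

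SAP 5 fixes the denominator of the AE percentages as the "number of participants in the considered analysis set and period/phase for a certain vaccination group".

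SAP 5.1.1 has a separate rule for solicited events: "In case no grades are available, the grading of the solicited events will occur according to the grading list in Attachment 1". It also makes solicited local events related by definition.

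SAP 5.1.2 lists the affected rows: Grade 3 solicited events, related solicited systemic events, unsolicited events with Grade 3 as worst grade, related unsolicited events and related SAEs. It plans listings or narratives for participants who, among other triggers, "experience a Grade 3 AE considered related to vaccination". SAEs, deaths and AEs leading to discontinuation of vaccination are separate triggers.

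Protocol 12.1.3 requires a severity grade for every AE. Protocol 12.3.1 requires every AE to be judged related or unrelated, with the investigator's opinion entered in the eCRF.

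**The concern.** The rule is presented as no imputation, but with a fixed denominator it has the effect of one. In the related and Grade 3 percentages, a participant whose only candidate event has a blank field is counted exactly like a participant without such an event. Protocol 12.1.2 reserves the unrelated category for events where "there is no suspicion that there is a relationship between the study vaccine and the adverse event". A blank field does not establish that.

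The SAP is more cautious about another missing AE field. Under Attachment 2, Step 1, an event with a completely missing start date goes to the post-dose 1 period, unless its end date shows that it was over before then. Missing timing thus counts towards vaccine exposure and missing causality counts away from it, with no reason given.

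Safety and reactogenicity are a secondary objective, and 90 participants per lot group were added to enlarge the safety database. The rows concerned are those in which single records matter most. The SAP plans no count of blanks, no missing category and no sensitivity table, so a reader of the tables cannot tell a true zero from a blank.

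**Working it through.** The documents give no figure for this point, so the check consists of the direction, the weight of one record, and an illustration under stated assumptions.

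**Direction.** Let N be all participants in the set and period (SAP 5), x the participants counted in a related or Grade 3 row, and m the participants whose only candidate event for that row has the field blank.

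- Reported rate: x/N.
- Highest rate compatible with the data: (x + m)/N.
- The rate with complete data lies between the two. A blank can remove a participant from x, can never add one, and never changes N. The two rates coincide if nothing is blank or if the participant has another event that qualifies.

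**Exceptions.**

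- Relatedness of solicited local events cannot fall, because SAP 5.1.1 sets it by definition. The solicited related tables are systemic only.
- The rows for Grade 1 or Grade 2 as worst grade can move either way. For example, a participant with one Grade 1 event and one ungraded event that was truly Grade 3 is added to the Grade 1 row.

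**Weight of one participant** (planned sizes from SAP Table 2).

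- Lot group: 1/234 = 0.43 percentage points.
- Group 5: 1/50 = 2.0 percentage points.
- For a rare outcome, with two-sided 95% Clopper-Pearson intervals: 1/234 (0.01% to 2.36%) becomes 0/234 (upper limit 1.56%), and 1/50 (0.05% to 10.65%) becomes 0/50 (upper limit 7.11%).

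**Illustration.** The counts and shares here are assumptions.

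- With 12 of 234 participants counted as Grade 3, the reported rate is 12/234 = 5.1%. If a further 1, 3 or 5 participants have only an ungraded event, the upper bound is 13/234 = 5.6%, 15/234 = 6.4% or 17/234 = 7.3%.
- With a true rate of 5% and a share q of those participants lost to blanks, the reported rate is 5% × (1 − q): 4.90%, 4.75%, 4.50% and 4.00% for q = 2%, 5%, 10% and 20%. At q = 0 it is 5%.

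**Listing and narrative trigger.** The related Grade 3 trigger needs both fields. A non-serious Grade 3 event with blank causality, or a non-serious related event with a blank grade, does not meet it. Unless another trigger applies, that participant drops out of the SAP's planned set.

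**SAP 5.1.1 against 5.1.4.** Take an ungraded solicited fever of 39.5 °C. The vital signs table in SAP Attachment 1 makes a temperature above 38.9 °C Grade 3, so under 5.1.1 the event receives a grade. Its severity is then no longer missing and 5.1.4 does not reach it. Most systemic items in Attachment 1 are functional scales that may not be gradable afterwards, so some ungraded solicited events could remain for 5.1.4. The SAP does not state this order.

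**The case against.** The strongest reply is that blanks should be rare. Grade and causality are mandatory, the sponsor reviews the eCRF for completeness and can raise queries (Protocol 17.5 and 17.6), and analyses run on locked databases. All collected unsolicited AEs are listed, so a blank does not hide the event itself. SAEs go to the sponsor within 24 hours on a form signed by a physician and are listed or narrated regardless of causality. Protocol 11.4 also allows, without requiring, listings or narratives for severe AEs with no condition on relatedness. No formal safety comparison is planned, so no decision rule turns on these rates. All of this stands, and it makes the point minor. It does not change the direction of the rule or make blanks visible in the tables.

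A second reply is that counting blanks as related merely replaces an error in one direction with an error in the other. That is fair as far as it goes. The difference is that the proposed count is cautious for a safety table and its size is disclosed.

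Three stronger readings are tempting, and the documents do not support them.

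- A reader might infer that SAP 5.1.1 and 5.1.4 contradict each other. They do not: the specific rule for solicited events can be applied first, and only the order is unstated.
- A reader might infer that a blank causality is reclassified as unrelated, against Protocol 12.1.2. The SAP says only that the relationship is not reported; it makes no causality judgement. The effect on the related count is nevertheless the same.
- A reader might infer that every related table loses events. Relatedness of solicited local events is unaffected.

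**Conclusion.** The point holds as a small defect in one direction. Under SAP 5.1.4 with the SAP 5 denominator, related rates for unsolicited AEs, SAEs and solicited systemic AEs, and Grade 3 rates, are at or below their complete-data values. A non-serious Grade 3 event with blank causality also misses the SAP's related Grade 3 trigger.

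The size per affected participant is 0.43 points in a lot group and 2.0 points in Group 5, on planned group sizes and assuming the participant has no other qualifying event. The total cannot be computed, because no rate of blanks is given, and it should be small because both fields are mandatory.

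The direction applies to the rate within each group. The rule covers placebo as well, so the documents do not show that differences between vaccine and placebo are biased in a particular direction, nor that any safety conclusion would change.

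**What to change.** Amend SAP 5.1.4 as follows.

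1. Count an AE whose relationship is still missing at database lock as related, both in the related rows and tables and in the related Grade 3 trigger. Give the number of such AEs per group in a footnote.
2. State that for solicited events the Attachment 1 grading in SAP 5.1.1 is applied first, and that 5.1.4 covers only events still ungraded after that.
3. Show any AE still ungraded in a grade-missing row of the worst-grade and Grade 3 tables. Include it in the related Grade 3 listing if it is related or its relationship is missing.

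The two fields are treated differently on purpose. Relationship has two levels, so a cautious value is available. Grade has three, and placing every ungraded event in Grade 3 would be a much stronger assumption than showing it separately.

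The cost is SAP wording and a few lines of programming, with no change to conduct or data collection. The downside is that a few events that may be unrelated are counted as related; the footnote shows how many.
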